#### **The Chief Investigator will:**

- Assess the event for seriousness, expectedness and relatedness to the study IMP
- Take appropriate medical action, which may include halting the trial and inform the Sponsor of such action
- If the event is deemed a SUSAR, shall, within seven days, enter the required data on the ICSR Submissions.
- Shall inform the REC using the reporting form found on the HRA web page within 7 days of knowledge of the event
- Shall, within a further eight days send any follow-up information and reports to the MHRA and REC.
- Make any amendments as required to the study protocol and inform the ethics and regulatory authorities as required

### 11.9 Trial Treatment Related SAEs

A serious adverse event that is unexpected in its severity and seriousness *and* deemed directly related to or suspected to be related to the trial treatment but not the IMPs shall be reported to the ethics committee that gave a favourable opinion as stated below.

**The event shall be reported immediately of knowledge of its occurrence to the Chief Investigator.**

#### **The Chief Investigator will:**

- Assess the event for seriousness, expectedness and relatedness to the trial treatment.
- Take appropriate medical action, which may include halting the trial and inform the Sponsor of such action.

- If the event is deemed related to the trial treatment shall inform the REC using the reporting form found on the Health Research Authority web page within 7 days of knowledge of the event.
- Shall, within a further eight days send any follow-up information and reports to the REC.
- Make any amendments as required to the trial protocol and inform the REC as required.

### **11.10 Participant removal from the study due to adverse events**

Any participant who experiences an adverse event may be withdrawn from the study at the discretion of the Investigator.

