## 7.6 Removal of participants from therapy or assessments

Everyone conducting or taking part in this trial should follow the PerSEVERE guiding principles [34] for clinical trial research:

1. Everyone running or taking part in the trial should be aware that participants may choose to change, reduce or stop their participation after they agree to join the trial.
2. The nature and extent of participation changes should be the participant's decision to make, within the limits of what is possible for the trial. Their decision should be informed and freely-given.
3. Everyone running or taking part in the trial should be aware that collecting as much as possible of the trial's planned data can help the trial reach a clear and reliable conclusion.
4. Loss of contact between a participant and researchers should not be considered the same as a participant saying that they want to stop the trial participation.
5. The trial data collection should continue until the trial participant explicitly tells researchers that they want it to stop.
6. Data collected for the trial up to the point the trial participant stops providing data should be used in the trial analysis, and kept with the other trial data until the trial is over.
7. Stopping participation early does not affect participants' right to receive the trial-related information later on, if they want to receive it or if it could be important for them to have.

Participants who become pregnant during the course of the trial will be withdrawn from the trial and should contact their GP for further direction regarding the pregnancy, and their managing clinician for advice on managing LS during pregnancy. The occurrence of pregnancy will be captured at site via the trial *Pregnancy Notification Form* on the trial database.

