
Discontinue follow-up questionnaires
	
Site will complete relevant e-CRFs and inform NCTU. Upon participant request to discontinue from trial questionnaires will be marked as withdrawn from questionnaire collection on the trial database and no further contact will be made with the participant for the purpose of obtaining questionnaire follow-up data. Clinic visits and data collection from medical notes will continue.
	
Any data collected prior to participant withdrawal will be retained and used. From the date of discontinuation onwards only following data will be collected:
 
 
- Number of flares
 
- Time to first flare
 
- Clinical photographs (if consented), VASS and examination
 
- Development of VIN or vulval SCC
 
- Global clinical severity assessment
 
- Vulval development and scarring (in adolescents and children)
 
- Adverse events
 
- Concomitant medication
 

Discontinue from two weekly notifications
	
Site will complete relevant e-CRF and inform NCTU as soon as possible. The trial treatment and ALL follow up data collection, apart from two weekly data collection, will continue
	
Any data collected prior to participant withdrawal will be retained and used. From the date of withdrawal onwards, only following data will be collected:
 
 
- Clinical photographs (if consented), VASS and clinical examination
 
- Development of VIN or vulval SCC
 
- Global clinical severity assessment
 
- Vulval development and scarring (in adolescents and children)
 
- Sexual function (adults only)
 
- Condition specific QoL - CDLQI for children and VQLI for adults
 
- Generic utility instrument (health related) – CHU-9D for children and EQ-5D-5L for adolescents/adults
 
- Adverse events
 
- Resource use
 
- Concomitant medication
 

--	---	--

The site team should make every effort to keep their contact with the trial participants, within the scope of this protocol, to collect as much as possible data that can help to answer the research question.

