## 8.8 Protocol Deviations and Violations

A protocol deviation can be defined as a move away from described procedures in the treatment regimen e.g. a missed dose, study visit missed or taking place later than planned leading to data collections being at time-points differing to the rest of the study population. Because PEARLS is a pragmatic trial, and the assessment windows are selected to mirror the clinical practice, delayed assessments will only be reportable routinely to the TMG/TSC but will not constitute towards protocol violations which will need to be reported immediately to the sponsor.

A protocol violation is a variation in practice from the protocol which will need to be assessed for their impact on safety of the trial participant and of the data integrity, because they:

- a. Reduce the quality or completeness of data (e.g. not using backups for database)
- b. Impact trial participant's safety, rights or welfare (e.g. randomising patient without prior consent or without fulfilling eligibility criteria, disclosing participants identifiable information to third parties without consent)

Protocol violations may on occasions lead to the protocol being altered via a substantial amendment or a trial participant being excluded from the trial.

Protocol deviations (apart from those deviated from assessment windows) and ALL violations must be reported immediately to the PEARLS Trial Office.

The CI will notify the Sponsor if a protocol or non-protocol violation has an impact, or a potential to have an impact, on participant safety or integrity of the trial data. The Sponsor will advise on appropriate measures to address the occurrence which may include reporting of a serious GCP, protocol, GDPR etc breach, internal audit of the trial and seeking counsel of the trial committees.

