## 10 STATISTICAL CONSIDERATIONS

### 10.1 Sample size and justification

Using data from a subset of 211 women with LS surveyed in preparation for the funding application for this trial who would be broadly eligible, the mean (SD) number of flares in this group was estimated to be 4.0 (2.8) per year. The data showed evidence of overdispersion (variance larger than the mean) hence a negative binomial regression would be appropriate for the data. Assuming an event rate of 4 flares per patient per year, a sample size of 320 would be required to detect a relative reduction of 25% in number of flares in the intervention group to 3 flares per patient per year (absolute reduction of 1 flare per patient in a year), with 90% power, 1:1 allocation and a two-sided significance level of 0.05, using dispersion parameter value of 0.34 estimated from the survey data. A relative reduction in number of symptom flares by 25% is considered meaningful by patients and clinicians since eligible patients have controlled LS so even a small reduction in number of flares would be meaningful to them. Loss to follow-up is expected to be around 5-10% [35-38]. Inflating the sample size by 20% to account for both non-collection of primary outcome data and treatment non-compliance, PEARLS aims to randomise 400 participants.

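### The pregnancy and adverse-event clauses end participation in the trial, not only treatment, against section 7.6's rule that data collection stops only when the participant says so

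*Protocol*

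**What the plan says.** **Principles.** Section 7.6 adopts guiding principles. Principle 2 makes changes in participation the participant's own decision, within what the trial can accommodate. Principle 5 reads: "The trial data collection should continue until the trial participant explicitly tells researchers that they want it to stop". Principle 6 keeps and uses data collected before someone stops. Section 10.2 sets an analysis by allocated strategy regardless of adherence, and section 10.7 aims to follow everyone to the primary endpoint.

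**Treatment-only route.** Table 5 in section 7.7 has a level for discontinuing trial treatment. It keeps number of flares, time to first flare, scarring assessments, VIN/SCC and adverse events. Section 7.8 says people who stop treatment will be asked to go on giving follow-up data.

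**Clauses that go further.**
- Pregnancy, section 7.6: "Participants who become pregnant during the course of the trial will be withdrawn from the trial and should contact their GP". Section 11.6 repeats this for either arm.
- Adverse events, section 11.10: "Any participant who experiences an adverse event may be withdrawn from the study at the discretion of the Investigator".
- Violations, section 8.8: "Protocol violations may on occasions lead to the protocol being altered via a substantial amendment or a trial participant being excluded from the trial".

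**Opting out of prompts.** For participants who decline the fortnightly notifications, Table 5 says: "The trial treatment and ALL follow up data collection, apart from two weekly data collection, will continue". The list beside it leaves out adherence and acceptability as well as the two flare outcomes.

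**The concern.** In the pregnancy and adverse-event clauses someone other than the participant ends participation, and what ends is the trial or study rather than the treatment. The nearest Table 5 level to leaving the trial is complete withdrawal, after which nothing more is collected. A site following section 11.10 literally could therefore stop flare reports and the 12- and 24-month assessments for a woman who is reachable and willing to continue.

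The adverse-event clause matters most. Site staff and investigators are unblinded (section 5.1, Table 4), and steroid exposure differs by arm by design. The targeted adverse events in section 11.4 include local burning, skin pain, pruritus and progression of scarring. The Synopsis footnote lists itching, burning and pain as symptoms of LS, and scarring progression is a secondary outcome. Section 11.5 also counts active LS not controlled by rescue therapy among its non-expedited serious events. Participants eligible for withdrawal under 11.10 may thus be the ones who are flaring or progressing.

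**Working it through.** **1. The passages side by side**

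| Event | Who decides | What ends, as worded | Table 5 level named | Agrees with principles 2 and 5? |
|---|---|---|---|---|
| Pregnancy (7.6, 11.6) | Protocol, mandatory | Trial | None | No |
| Adverse event (11.10) | Investigator, discretionary | Study | None | No |
| Violation (8.8) | Not stated | Trial | None | Unclear; the examples include randomisation without consent |
| Declines prompts (Table 5) | Participant | Fortnightly flare reports | Its own row | Yes |

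Section 11.4 has targeted adverse events followed until resolution or stabilisation, or until the trial treatment is shown not to be the cause. That sits badly with leaving the study because of the same event.

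**2. The prompts row.** Its list equals the list for discontinuing trial treatment minus the two flare items. Adherence and acceptability can sensibly drop out when treatment stops, but here treatment continues and the row says all other collection continues. The row contradicts itself.

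**3. The plan's own sample size.** Inputs from section 10.1: "Assuming an event rate of 4 flares per patient per year"; "a relative reduction of 25% in number of flares in the intervention group to 3 flares per patient per year"; "with 90% power, 1:1 allocation and a two-sided significance level of 0.05"; dispersion 0.34. For two negative binomial rates over one year:

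- Variance under the alternative: V1 = 1/4 + 1/3 + 2 × 0.34 = 1.2633.
- Variance under the null, pooled rate 3.5: V0 = 2/3.5 + 2 × 0.34 = 1.2514.
- n per arm = (1.960 × √V0 + 1.282 × √V1)² / (ln 0.75)² = 159.5, so 160 per arm and 320 in all.
- 320 / (1 − 0.20) = 400.

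Both stated figures reproduce. The sample size is sound, and this point does not rest on it.

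**4. Precision lost (illustration).** Assume a share f of both arms stops flare reporting at 6 months, with the earlier data kept. Information per arm at rate μ, with k = 0.34, is n[(1−f)·μ/(1+kμ) + f·0.5μ/(1+0.5kμ)]. The variance of the log rate ratio is 1/I(4) + 1/I(3), and power is Φ(0.2877/SE − 1.960).

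| f | 400 randomised | 320 analysed |
|---|---|---|
| 0 | 95.2% | 89.9% |
| 5% | 94.9% | 89.5% |
| 10% | 94.5% | 89.0% |
| 20% | 93.9% | 88.0% |

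The loss of power is small.

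**5. Bias from informative stopping (illustration).** Assume a share f of the reactive arm flares at r times the rate of the others and stops at time t (in years), the arm's true mean being 4. The others' rate is b = 4/((1−f) + f·r). The observed crude rate is [(1−f)·b + f·r·b·t] / [(1−f) + f·t].

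- f = 2%, r = 1.5, t = 0.5: b = 3.960, observed 3.980, rate ratio 3/3.980 = 0.754.
- f = 5%, r = 2, t = 0.25: observed 3.859, rate ratio 0.777.
- f = 10%, r = 2, t = 0.25: b = 3.636, observed 3.455/0.925 = 3.735, rate ratio 0.803.

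Over f from 2% to 10%, r of 1.5 or 2 and t of 0.25 or 0.5, a true 0.75 appears as 0.754 to 0.803. If the high-flare leavers were in the proactive arm instead, the bias would run the other way. The protocol gives no figure for f, r or t.

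**The case against.** The defence has several sound points.

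- **The analysis itself stays as allocated.** A reader might infer that withdrawn participants are dropped and intention-to-treat is broken. The document says otherwise: data before withdrawal are retained and used, and the model takes exposure time. What fails is follow-up after the event. The exposure term deals with that only if stopping is unrelated to flare rate.
- **The wording is loose rather than decisive.** Section 11.10 is permissive and names no Table 5 level, section 7.7 tells sites to make every effort to keep contact, and principle 2 is limited to what the trial can accommodate. This is fair, but it leaves the choice to each unblinded site, and the pregnancy clause is not permissive.
- **Pregnancy will probably affect few.** Contraception is required of participants of child-bearing potential, incidence peaks in childhood and after the menopause, and nothing suggests that it depends on arm. This stands: the clause conflicts with the principles but is a minor source of bias.
- **Opting out of prompts is the participant's own choice.** It is tempting to list it as a further contradiction. It breaks no principle, and the primary endpoint is defined by the fortnightly reports, so a count recalled at a visit is a different measurement. Only the incomplete list is an error.
- **Violations include randomisation without consent.** A blanket rule keeping every violator in follow-up would be wrong. This stands, and it limits what should be written in 8.8.

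**Conclusion.** The point holds as a conflict between clauses. Sections 7.6, 11.6 and 11.10 allow or require removal from the trial where the section 7.6 principles reserve that decision to the participant and where a treatment-only level already exists. Later flare, scarring and VIN/SCC data are put at risk. For adverse events the loss may be informative; its size and direction are not known from the document, and the 0.754 to 0.803 range rests wholly on the assumptions in the working. No statistical analysis plan can recover data that sites were told not to collect.

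A reader might also infer a gain in power: if the whole 20% allowance were non-collection and half could be recovered, 160 per arm would become 180, and Φ(0.2877/√(1.2633/180) − 1.960) = 93% against 90%. The document does not support that. The 20% covers non-compliance as well, loss to follow-up is expected at only 5-10%, the recoverable half has no source, and people who leave part-way still contribute data. Recalled counts confined to a sensitivity analysis could not raise the power of the main analysis in any case.

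The prompts row in Table 5 is a separate drafting error: its list contradicts its own statement. It matters because adherence feeds the planned complier analyses.

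**What to change.** 1. **Sections 7.6, 11.6 and 11.10.** Reconcile these with the principles and with Table 5. State that a participant whose treatment is stopped moves to the Table 5 level for discontinuing trial treatment and that, whatever is decided about treatment, she stays in follow-up unless she declines data collection. No view is taken here on when treatment should stop.
2. **Section 8.8.** State that a violation does not by itself remove a validly consented, randomised participant from follow-up or from the as-allocated analysis.
3. **Table 5, row for discontinuing two-weekly notifications.** Add adherence and acceptability to the list.
4. **Optional.** For participants who decline the prompts but still attend, ask at 3, 6 and 12 months for the number of flares since the last visit, labelled as recall and used only in a sensitivity analysis. This is an improvement, not the correction of a contradiction.

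Items 1 to 3 cost protocol wording and matching changes to site instructions and withdrawal forms. Item 4 costs one e-CRF question, and its downside is coarser, recalled data.

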## **12 HEALTH ECONOMIC EVALUATION**

There is a scarcity of economic evidence to help inform decisions about the efficient management and treatment of LS. This economic evaluation will therefore be important not only in providing evidence on value for money of the specific interventions evaluated but also on providing evidence around the range of costs incurred by people with LS and the validity of utility instruments for this condition.

An incremental cost analysis will be conducted from an NHS and Personal Social Services (PSS) perspective in the primary analysis capturing the intervention resource use and wider health resource use related to LS (including any related to adverse effects) throughout the trial period. In addition to an NHS and PSS perspective, but presented separately, an estimate of out-of-pocket and time costs of managing LS for participants and parents/guardians (where appropriate) will be recorded. Intervention costs will be recorded during the trial through e-CRFs and wider health care resource costs associated with LS will be estimated using resource use data captured in participant questionnaires at baseline, 3, 6, 12, 18 and 24 months. Resource use will be valued using published unit costs or participant reported estimates for a common recent price year.

We will undertake a cost effectiveness analysis as the primary analysis because it will enable us to analyse all participants together, irrespective of age. Using the primary outcome measure we will estimate the incremental cost per flare averted. However, it will mean decision makers will need to make a value judgement about the acceptable value of the cost per flare averted. The use of available generic utility instruments in LS is under-researched such that it is unclear how well they capture the health-related quality of life aspects of people living with LS. Research to explore the measurement properties of the EQ-5D and CHU-9D in this patient group would be useful and therefore, as a secondary analysis we will conduct two cost-utility analyses estimating incremental cost per quality-adjusted life years (QALY) based on age to reflect the utility instrument used. Utility will be measured at baseline, 3, 6, 12, 18 and 24 months using the EQ-5D -5L [40, 41] (for adults and children aged 12 years or over) and CHU -9D [42-44] (for children aged 5 -11 years, where for participants aged 5-6 years old the CHU-9D will be completed by parental proxy, but for all other ages will be self-completed) questionnaires, which will be used to estimate the quality-adjusted life years over the study period using linear interpolation and area under the curve analysis

with and without baseline adjustment [45]. Separate cost utility analyses will be presented for those aged 12 years and over, using the EQ-5D-5L to estimate QALYs and for those aged under 12 years using the CHU-9D (where participants complete the same utility instrument throughout the study based on their age at baseline). The rationale for using the EQ-5D-5L is based upon the EUROQOL EQ-5D-Y user guide ([https://euroqol.org/wp-content/uploads/2016/09/EQ-5D-Y\\_User\\_Guide\\_v1.0\\_2014.pdf](https://euroqol.org/wp-content/uploads/2016/09/EQ-5D-Y_User_Guide_v1.0_2014.pdf)), which states that although the EQ-5D-Y “is generally recommended” the adult version might be possible in older children. Using just the one version of the EQ-5D will enable consistency, the EQ-5D-Y also does not currently have a UK valuation set. The CHU-9D was chosen over the EQ-5D-Y because a UK valuation set exists for it. The EQ-5D will be analysed in line with recommendations at the time of analysis [46].

Where appropriate (i.e. in the absence of either intervention dominating) the incremental cost effectiveness of proactive maintenance therapy compared to reactive treatment will be estimated by dividing the difference in costs by the difference in outcomes (number of flares in the cost effectiveness analysis and QALYs in the secondary cost-utility analysis) using a regression based approach such as seemingly unrelated regression analysis if assumptions hold and using multiple imputation methods to take account of missing data. Decision uncertainty will be presented via Cost-Effectiveness Acceptability Curves (CEACs) based on non-parametric bootstrapping of cost and effect pairs [47, 48]. We will write a detailed health economics analysis plan, in advance of database lock that will be reviewed by other study team members and another health economist, to include a section on planned sensitivity analyses. Sensitivity analyses will be undertaken to explore key uncertainties around important parameters in the economic evaluation. This might include, for instance, the impact of missing data and how this is handled in the analysis, using recommended methods [49], should missing data be found to be an issue; the impact of taking a wider perspective beyond the NHS and PSS taken in the primary analysis; and the impact of adherence to treatment on cost-effectiveness. These sensitivity analyses will be presented in a way that aids understanding about the interpretation of cost-effectiveness results.

Given the paucity of evidence for reactive and proactive treatment and the longer-term outcomes for people with LS we do not propose to undertake longer term cost-effectiveness modelling as part of this trial but this is something that would be worth considering in future when the results of this study are known and when longer term data around the impact of maintenance regimes on malignancy rates becomes available. This within-trial economic evaluation will provide robust trial evidence to inform longer term modelling in due course and decision makers about the likely short-term (two year) cost-effectiveness of interventions for LS, in particular about whether proactive or reactive treatment offers greater value for money.

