### 4.3 Primary endpoint

Number of flares over 12 months. Flare is defined as worsening of symptoms requiring increased application of TCSs as reported by participants via two weekly reminders.

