## 7.5 Expected duration of participant participation

Trial participation for individual participants will last for 24 months.

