### Follow up between clinic visits

Number of flares (primary outcome) and time to first flare (secondary outcome) will be captured throughout the first 12 months of the study. The primary outcome will be collected every two weeks via text/email/app (as per participant preference). An automated text message/email/app notification prompt will be sent to remind participants to complete their data entry with reminders for those who have not completed. The data collected via these methods will be linked to a web-browser page which is a direct interface to the trial database, REDCap. For the small proportion of patients who do not have a smartphone or computer, a member of the research team will telephone call to collect the information.

### Visit 2

(at 3 months)

- EQ-5D-5L in adolescents/adults and CHU-9D in children
- Condition specific Quality of Life will be assessed via VLQI or CDLQI
- Clinical global severity assessment – assessed by treating clinician
- Vulval development and scarring (in adolescents and children)
- Concomitant medication (relevant to condition)
- Bespoke resource use questionnaire and healthcare questionnaire
- Adherence to treatment
- Change or cessation of therapy
- Adverse events

### Visit 3

(at 6 months)

- EQ-5D-5L in adolescents/adults and CHU-9D in children
- Condition specific Quality of Life will be assessed via VLQI or CDLQI
- Clinical global severity assessment – assessed by treating clinician
- Vulval development and scarring (in adolescents and children)
- Concomitant medication (relevant to condition)
- Bespoke resource use questionnaire and healthcare questionnaire
- Adherence to treatment
- Change or cessation of therapy
- Adverse events

### Visit 4

(at 12 months)

- EQ-5D-5L in adolescents/adults and CHU-9D in children
- Condition specific Quality of Life will be assessed via VLQI or CDLQI
- Clinical global severity assessment - assessed by treating clinician and blinded assessor
- Vulval development and scarring (in adolescents and children)
- Concomitant medication (relevant to condition)
- Bespoke resource use questionnaire and healthcare questionnaire
- Adherence to treatment
- Change or cessation of therapy
- Adverse events
- Scarring (VASS and examination) – by blinded assessor
- Acceptability of treatment
- Sexual function using Female Sexual Function Index (in adults only)

### Visit 5

(at 18 months)

- EQ-5D-5L in adults and CHU-9D in children

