## 8.7 Trial assessments\*

Table 7. Data collection timepoints

Trial assessment	Source	Timepoint and visit number					
		Screening/baseline Visit 1	3 month Visit 2	6 month Visit 3	12 month Visit 4	18 month Visit 5	24 month Visit 6
Confirmation of eligibility	Medical notes/clinician/participant	X					
Consent	Participant	X					
Randomisation	Participant	X					
Medical history	Participant/medical notes	X					
Demographic information	Participant/medical notes	X					
Concomitant medication (relevant to condition only)	Participant	X	X	X	X	X	X
Number of flares and time to 1st flare	Participant	Starting 2 weeks from randomisation, every 2 weeks for 12 months					
Progression of scarring via photograph (optional), VASS and examination	Clinician	X **			X €		X €
Vulval development and scarring (adolescents and children)	X	X	X	X	X	X	X
Clinical global severity assessment	Clinician	X	X	X	X μ	X	X μ
Condition specific Quality of Life (VQLI or CDLQI)	Participant	X	X	X	X	X	X
Health related quality of life (generic utility instrument) (EQ-5D-5L in adolescents/adults or CHU-9D in children)	Participant	X	X	X	X	X	X
Sexual function using Female Sexual Function Index (adults only)	Participant				X		X
Acceptability of treatment	Participant				X		X
Adherence to treatment	Participant		X	X	X	X	X
Resource use (bespoke and healthcare)	Participant	X	X	X	X	X	X
VIN or vulval SCC	Clinician						X
Adverse effects of therapy	Participant, Clinician		X	X	X	X	X
Change/cessation of therapy	Participant		X	X	X	X	X
* Definition of age groups for purpose of assessments is described in section 4.4		° At 12 and 24 months assessed by blinded assessor					
** Assessed by photographs (if consented) or clinical assessment diagram		μ At 12 and 24 months assessed by treating clinician and blinded assessor					
€ Clinical assessment comparing to baseline photographs (if consent given for photographs) or to baseline clinical assessment diagram if consent for photographs not obtained							

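### As written, the primary cost-per-flare analysis sets costs from the whole 24-month trial period against flares counted for 12 months only

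*Protocol*

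**What the plan says.** **Which analysis is primary.** The Synopsis (Health economics) and section 12 both name the all-age cost-effectiveness analysis, from an NHS and PSS perspective, as the primary economic analysis. Section 12 defines its effect measure: "Using the primary outcome measure we will estimate the incremental cost per flare averted".

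**Effect window.** Section 4.3 defines that outcome as "Number of flares over 12 months". Section 8.1 (Follow up between clinic visits) says flare data "will be captured throughout the first 12 months of the study", and Table 7 in section 8.7 gives the schedule as "Starting 2 weeks from randomisation, every 2 weeks for 12 months".

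**Cost window.** For the primary analysis, section 12 counts intervention resource use and "wider health resource use related to LS (including any related to adverse effects) throughout the trial period". The wider costs come from "resource use data captured in participant questionnaires at baseline, 3, 6, 12, 18 and 24 months". Section 7.5 fixes the length of that period: "Trial participation for individual participants will last for 24 months".

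**Ratio and label.** Section 12 forms the ratio of the between-arm difference in cost to the between-arm difference in number of flares, wherever neither strategy dominates. It closes by saying that the evaluation will inform decision makers about the "short-term (two year) cost-effectiveness of interventions for LS".

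**The concern.** A cost-effectiveness ratio can be interpreted only if cost and effect are accumulated over the same period. Here year-2 costs enter the numerator, while flares averted in year 2 cannot enter the denominator because nobody records them. Year-2 costs can be expected to differ between arms, since section 8 has the proactive regimen prescribed for 24 months.

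Section 12 acknowledges that no accepted value exists for a flare averted and leaves that judgement to decision makers. They would be judging the absolute size of this ratio, which is what a mixed horizon distorts. The cost-effectiveness acceptability curve is bootstrapped from the same cost and effect pairs, so it inherits the mismatch.

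**Working it through.** The protocol states no cost per flare, so there is no figure of its own to reproduce. The check has two parts.

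**1. Do the texts really pair the two windows?**

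| Term | Window | Source |
|---|---|---|
| Costs, primary analysis | whole trial period, 24 months | sections 12 and 7.5 |
| Flares, primary outcome | 12 months | sections 4.3, 8.1 and 8.7 |
| Label on the evaluation | two years | section 12 |

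Section 12 attaches the trial-period cost window to the primary analysis by name, and the Synopsis identifies that analysis as the cost per flare averted. No sentence cuts the costs at 12 months for this ratio, and none extrapolates flares to 24 months.

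**2. What does the pairing do to the ratio?**

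Let c1 and c2 be the incremental cost of proactive over reactive treatment in years 1 and 2. Let d1 and d2 be the flares averted per participant in those years.

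- As written: R = (c1 + c2) / d1
- Matched at 12 months: R12 = c1 / d1, so R / R12 = 1 + c2/c1
- Matched at 24 months: R24 = (c1 + c2) / (d1 + d2), so R / R24 = 1 + d2/d1

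The only input the protocol supplies is the design effect in section 10.1: 4 − 3 = 1 flare averted per participant in a year, so d1 = 1. It gives no c1, c2 or d2. The year-2 to year-1 ratio r (c2/c1 or d2/d1, according to the comparator) is therefore an assumption:

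| Assumed r | Factor 1 + r |
|---|---|
| −0.5 | 0.5 |
| 0 | 1.0 |
| 0.5 | 1.5 |
| 1 | 2.0 |
| 1.5 | 2.5 |

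If r is below −1, the factor is negative and the ratio changes sign. This happens, for example, if savings in year 2 exceed the extra cost of year 1.

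Worked case with equal years (c1 = c2 = c, d1 = d2 = 1): R = 2c/1 = 2c, R12 = c/1 = c, and R24 = 2c/2 = c. The mixed ratio is twice the matched one on either horizon.

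For the acceptability curve, expected net benefit at a value λ per flare is λ·d1 − (c1 + c2). It crosses zero at λ = (c1 + c2)/d1, whereas on a matched 12-month basis it crosses at c1/d1. The shift is the same factor, 1 + c2/c1.

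**The case against.** The best defence is that no single sentence says 24-month costs will be divided by 12-month flares. One cost dataset serves three analyses, and the two cost-utility analyses need costs to 24 months. On this view, invoking the primary outcome could imply a 12-month analysis, the two-year phrase describes the evaluation as a whole in contrast to long-term modelling, and the promised health economics analysis plan will set the horizon.

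Part of this stands. The two-year phrase does cover the evaluation generally, and the plan is due before database lock, so nothing has been lost yet. But section 12 does not leave the cost window open: it assigns the trial period to the primary analysis specifically. A plan that follows the protocol reproduces the mismatch, and a plan that corrects it departs from the protocol. This is therefore a stated inconsistency and not a detail left for later.

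The objection to size stands in full. A reader might infer that the result will be about twice too high, or that it must be wrong on both horizons. The documents support neither. Twofold is only the equal-years case and is not a ceiling. With no incremental cost in year 2 the figure equals the matched 12-month ratio, and with no flares averted in year 2 it equals the matched 24-month ratio. If one strategy dominates, section 12 computes no ratio at all.

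**Conclusion.** The mismatch is in the current text: the primary cost-per-flare ratio has a 24-month numerator and a 12-month denominator, within an evaluation described as two-year. Its size cannot be stated from the protocol. The factor is 1 + c2/c1 against a 12-month ratio and 1 + d2/d1 against a 24-month ratio, and it depends wholly on what is assumed about year 2.

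Severity is moderate. Cost-effectiveness is a secondary objective. The clinical primary analysis and sample size are untouched, and the cost-utility analyses are already matched because utilities and costs both run to 24 months. It still affects the analysis designated as the main economic result, so it should be settled before database lock.

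**What to change.** In section 12 and in the health economics analysis plan:

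- Set the base-case cost-per-flare analysis to a 12-month horizon for both costs and flares. Resource use, including prescriptions, is already scheduled at 3, 6 and 12 months.
- Keep the 24-month horizon for the two cost-utility analyses, and limit the two-year wording to them.
- If a 24-month cost per flare is wanted, present it as a labelled sensitivity analysis and state how flares are extrapolated beyond month 12, for example with no, half and full persistence of the year-1 effect.

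The cost is a change of wording, with no new data collection. The downside is that the base-case per-flare result then says nothing about year 2. An observed 24-month figure would require flare collection to continue past 12 months.
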